14 STATISTICAL CONSIDERATIONS

14.1 Samples Size

Up to 30 subjects will receive up to two doses with NKA. As this is an early Phase II safety and efficacy study, formal sample size calculations were not performed. The planned sample size allows for a preliminary characterization of the safety profile of the NKA in patients with chronic kidney disease.

14.2 Analysis Objectives

The **primary objective** of the study is to assess the safety and efficacy of NKA injected in one recipient kidney and determine if two injections of NKA provide stabilization of renal function.

- Primary Safety Outcome Measures: procedure and/or product related adverse events (AE's) through 12 months following the initial NKA injection.
- Primary Efficacy Outcome Measures: serial measurement of serum creatinine and estimation of GFR through 6 months following the second cell injection

The secondary objective of the study is to assess the safety and tolerability of NKA administration by assessing renal-specific adverse events over a 12 month period following a patient's first NKA injection.

• Secondary Safety and Tolerability Outcome Measures: renal-specific laboratory assessments through 12 months following the last NKA injection under this protocol, whether first or second.

The **exploratory objectives** of the study are designed to assess the impact of NKA on renal function over a 12 month period following the initial NKA injection.

• Exploratory Outcome Measures: clinical diagnostic and laboratory assessments of renal structure and function (including eGFR, serum creatinine, and proteinuria) to assess changes in the rate of progression of renal disease; and effect of method of injection on these parameters.

Exploratory quality of life outcome measure will be the Kidney Disease Quality of Life survey obtained at baseline and at 1, 3, 6, 7, 9, 12, 15, 18, 30, and 42 months after a patient's first NKA injection.

Additional exploratory endpoints include the following:

- Changes from baseline in BUN, $_{\beta}2$ microglobulin and intact parathyroid hormone (iPTH) at 6 and 12 months post-injection.
- Changes from baseline in C-reactive protein (CRP) at 6 and 12 months post-injection.
- Need for initiation of renal replacement therapy.
- Comparison of pre-injection versus post-injection split functional differences between the left and right kidney based on renal scintigraphy.
- Comparison of pre-injection and post-injection kidney volume estimates based on comparative MRI assessments.
- Changes in the patient's perception of quality of life, as measured by serial KDQoL surveys.

14.3 Endpoints

The primary endpoint of the study is to assess the safety and efficacy of NKA injected in one recipient kidney and determine if two injections of NKA provide stabilization of renal function.

- Primary Safety Outcome Measures: procedure and/or product related adverse events (AE's) through 12 months following the initial NKA injection.
- Primary Efficacy Outcome Measures: serial measurement of serum creatinine and estimation of GFR through 6 months following the second cell injection

Secondary Endpoint

The secondary endpoint of the study is to assess the safety and tolerability of NKA administration by assessing renal-specific adverse events over a 12 month period following a patient's first NKA injection.

• Secondary Safety and Tolerability Outcome Measures: renal-specific laboratory assessments through 12 months following the last NKA injection under this protocol, whether first or second.

Exploratory Endpoints

The exploratory endpoint of the study are designed to assess the impact of NKA on renal function over a 12 month period following the initial NKA injection.

• Exploratory Outcome Measures: clinical diagnostic and laboratory assessments of renal structure and function (including eGFR, serum creatinine, and proteinuria) to assess changes in the rate of progression of renal disease; and effect of method of injection on these parameters.

Exploratory quality of life outcome measure will be the Kidney Disease Quality of Life survey obtained at baseline and at 1, 3, 6, 7, 9, 12, 15, 18, 30, and 42 months after a patient's first NKA injection.

- Changes from baseline in BUN, $_{\beta}2$ microglobulin and intact parathyroid hormone (iPTH) at 6 and 12 months post-injection.
- Changes from baseline in C-reactive protein (CRP) at 6 and 12 months post-injection.
- Need for initiation of renal replacement therapy.
- Comparison of pre-injection versus post-injection split functional differences between the left and right kidney based on renal scintigraphy.
- Comparison of pre-injection and post-injection kidney volume estimates based on comparative MRI assessments.
- Subgroup analyses will compare patients receiving a single injection with patients receiving two injections, and patients receiving laparoscopic injections with patients receiving percutaneous injections.

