2 PROTOCOL SYNOPSIS

Title: A Phase II, Open-Label Safety and Efficacy Study of an Autologous Neo-Kidney Augment (NKA) in Patients With Type 2 Diabetes and Chronic Kidney Disease (RMCL-CL001)

Therapeutic Product: NKA is made from expanded autologous selected renal cell population (SRC) obtained from the patient's kidney biopsy. To manufacture NKA, kidney biopsy tissue from each enrolled patient will be sent to Twin City Bio, LLC, Winston Salem, North Carolina, where renal cells will be expanded and SRC selected. SRC will be formulated in a gelatin based hydrogel at a concentration of 100 x 10^6 cells/mL, packaged in a 10 mL syringe, and shipped to the clinical site for use.

Study Objectives:

Primary Objective: The primary objective of the study is to assess the safety and efficacy of NKA injected in one recipient kidney and determine if two injections of NKA provide stabilization of renal function.

- Primary Safety Outcome Measures: procedure and/or product related adverse events (AE's) through 12 months following the initial NKA injection.
- Primary Efficacy Outcome Measures: serial measurement of serum creatinine and estimation of GFR through 6 months following the second cell injection

Secondary Objective: The secondary objective of the study is to assess the safety and tolerability of NKA administration by assessing renal-specific adverse events over a 12 month period following a patient's first NKA injection.

• Secondary Safety and Tolerability Outcome Measures: renal-specific laboratory assessments through 12 months following the last NKA injection under this protocol, whether first or second.

Exploratory Objective: Exploratory objectives of the study are designed to assess the impact of NKA on renal function over a 12 month period following the initial NKA injection.

- Exploratory Outcome Measures: clinical diagnostic and laboratory assessments of renal structure and function (including eGFR, serum creatinine, and proteinuria) to assess changes in the rate of progression of renal disease; and effect of method of injection on these parameters.
- Exploratory quality of life outcome measure will be the Kidney Disease Quality of Life survey obtained at baseline and at 1, 3, 6, 7, 9, 12, 15, 18, 30, and 42 months after a patient's first NKA injection.

Study Design: Multi-center, prospective, open-label, single-group study. All enrolled subjects will be treated with up to two injections of NKA at least 6 months apart.

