It is anticipated that all patients will be planned to receive 2 injections under this protocol, in order to allow dose-finding and to understand the duration of effect. Under certain circumstances a patient or investigator may decide to postpone or withhold the second dose. In general, if there appears to be any untoward safety risk, in situations including rapid deterioration of renal function, the development of uncontrolled diabetes, or the development of uncontrolled hypertension, or if there is the intercurrent development of a malignancy, the patient should not receive the second dose.

Second injections under this protocol will be staggered so that single injections in different patients occur no less than 3 weeks apart. The DSMB will review the clinical data regarding each of the first 3 second injections under this protocol, and will consult with the Sponsor before the 2nd, 3rd, and 4th second injections are made. Subsequent second injections will continue to be staggered so as to occur no less than 3 weeks apart, but individual DMSB review will not be required.

No staggering will be required for first NKA injections under this protocol.

Post-Injection Follow-up: Subjects will return to the clinic for follow-up safety assessments on Days 7, 14, and 28 post-injection and at 2, 3, and 6 months post-injection. At 6 months post-injection, post-treatment MRI and renal scintigraphy studies will be conducted. After patients complete the 6 month efficacy visit, they will be considered for a second NKA injection. Patients receiving a second dose will follow the same follow up visits that occurred after first injection. Patients 6 month post first injection visit will serve as the patients 14 to 10 day pre- second injection visit. Patients will return for their second injection and at 2, 3, and 6 months post-injection Patients will be followed up to 18 months in the post follow up phase with 6 months after first NKA injection and 12 months after second NKA injection. Refer to the time and events schedule on page 14 for additional post follow up time points.

Long Term Follow-up: Patients will be followed for safety and efficacy for 24 months after the 18 month initial follow up period. Telephone contact will be made 24 and 36 months after the last NKA injection, and visits will be made at 30 and 42 months after the last NKA injection.

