6.3.4 Phase One Clinical Trials – Interim Results

In April 2013, a first-in-human (FIH) clinical trial was initiated at the Karolinska University Hospital Huddinge in Stockholm, Sweden, by Tengion, Inc. The trial was a Phase 1, open-label, safety and injection optimization study of NKA injected into patients with CKD. NKA was manufactured from SRC obtained from a patient's biopsy, formulated with gelatin biomaterial, and injected back into the patient's left kidney. The primary objective of the study was to assess the safety and optimal injection of NKA injected at one site in a recipient kidney as measured by procedure and/or product related adverse events (AEs) through 12 months post-injection. The secondary objective of the study was to assess changes in renal function over a 12 month period following injection as measured by laboratory assessments. Six patients, recruited from the patient population at Karolinska University Hospital, were enrolled into the study. Each patient's baseline rate of disease progression has been used as the control to monitor for adverse changes in the rate of disease progression following injection. The study was terminated due to a lack of funding on December 10, 2014.

The patients enrolled in the Swedish study were recruited from the clinical practice at the Karolinska Institute and they continue to be closely monitored by the investigators. When RegenMed (Cayman) Ltd. establishes regulatory and ethics committee approval to continue the clinical trial, the patients will be re-consented and further safety and efficacy data compiled, and the opportunity to receive a second injection of NKA offered.

After the Swedish study had been under way, an IND for NKA was opened and a similar study started in the US, with one patient enrolled and treated at the University of North Carolina before the study was terminated due to a lack of funding on December 10, 2014.

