Ten to 14 days before the scheduled injection, the patient should report to the clinic for a preinjection qualification visit including final review of I/E criteria and a renal scintigraphy study. If the patient is still eligible for injection, the site will notify Twin City Bio LLC to manufacture NKA product from frozen renal cells. On the day of injection (Day 0), the patient should be admitted to the hospital and receive an NKA injection into the left (i.e., biopsied) kidney. For injection, the kidney will be accessed either (a) laparoscopic approach, or (b) using a percutaneous approach. The patient will remain in the hospital for two to four nights following the laparoscopic procedure, or 0-1 night following the percutaneous procedure, for observation and safety assessments. The patient should not be discharged until any procedure- and/or product-related AE's which may have occurred have stabilized or resolved.

Post-injection Follow-up: Subjects will return to the clinic for follow-up safety assessments on Days 7, 14, and 28 post-injection and at 3, 6, 9, and 12 months post-injection. At 6 months post-injection, post-treatment MRI and renal scintigraphy studies will be conducted. After patients complete the 6 month efficacy visit, they will be considered for a second NKA injection. Patients receiving a second dose will follow the same follow up visits that occurred after first dose. Patients 6 month post first injection visit will serve as the patients 14 to 10 day pre- second injection visit. Patients will return for their second injection and at 2, 3, and 6 months post-second injection. Patients will be followed up to 18 months in the post follow up phase with 6 months after first NKA injection and 12 months after second NKA injection. Refer to the time and events schedule on page 14 for additional post follow up time points. Subjects will complete an End-of-Study visit when they discontinue from the study or (for those who complete the study) at 18 months post-second injection.

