Discharge: After an injection via the percutaneous route, the patient may be discharged the same day if that is the site's usual practice after similar procedures (i.e. percutaneous ablation), after no less than 2 hours of observation and monitoring. If product- or procedure-related AE's occurred following surgery, the patient should not be released from the hospital until the AE's have either resolved, stabilized, or returned to baseline. After a laparoscopic injection, the patient should be observed in hospital for 2 to 4 nights to assess for AEs.

11.4 Follow-up (Days 7, 14, and 28, 2month, 3month, 6month ± 3 days first injection and second injection)

The patient should return to the clinic for follow-up visits one week after injection (Day 7) and on Days 14 and 28. The patient should make every attempt to return for the first follow-up visit on the protocol-specified day (i.e., Day 7) although a 3 day window will be allowed in the case of extenuating circumstances. A 3-day window is allowable for visits on Days 14 and 28, and on Months 2, 3, 6, and 12. At Month 6 visit the same procedures as the pre-injection visit should occur to prepare for the second injection of NKA, if the patient and investigator wish to proceed. The month 6 visit should occur -14 to -10 days before second injection and within 3 days of 6 months post first injection. Patients will return to the clinic Days 7, 14, and 28 after second injection and Months 2, 3, 6, 9, and 12 after second injection.

The monthly visit dates should be calculated using the calendar date of injection. For example, if the patient was injected on April 30^{th} , then the protocol-specified date of the 2 month follow-up visit would be June 30^{th} and the 3 month visit date would be July 30^{th} , etc. The visit window for the long-term monthly follow-up visits is ± 7 days.

End-of-Study Visit (EOS): Patients will complete the EOS Visit as noted below:

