- If a patient discontinues the study after having the biopsy but before injection, then he/she should complete all EOS assessments except for the imaging studies; the MRI and/or renal scintigraphy should only be performed if the PI feels one and/or the other would provide critical safety information needed for management of the patient. If the patient has an ongoing study procedure-related SAE, then the patient should not be discontinued until the SAE has resolved, stabilized, or returned to baseline. If the SAE continues for 18 months, then the patient should be discontinued from the study at 18 months and followed as discussed in Section 13.3.3.
- If a patient discontinues from the study after injection but before completing all of the protocol-specified follow-up visits, then he/she should have the EOS Visit at the time of discontinuation. For these patients, the PI will determine whether or not it is clinically prudent to perform one or both of the imaging studies (i.e., MRI and renal scintigraphy). If the patient has a procedure- or product-related SAE(s) that is ongoing, the patient should not be discontinued until the SAE(s) has resolved, stabilized, or returned to baseline. If the SAE(s) is still ongoing at the time of the 18 month visit, the subject should be discontinued from the clinical trial and the SAE followed as discussed in Section 13.3.3.
- Patients who complete all visits including all of the follow-up visits will return at 18 months following second injection for the EOS visit. If the patient has any procedure- or product-related SAE's that are ongoing at the 18 month visit (i.e., not resolved, stabilized

or returned to baseline) the subject should be discontinued from the clinical trial and the SAE followed as discussed in Section 13.3.3.

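### For new patients injected twice, the primary safety outcome covers at most 6 of the 12 months of follow-up planned after the second injection

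*Combined protocol and SAP*

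**What the plan says.** The primary safety outcome has the same end in the synopsis and in sections 7.1, 14.2 and 14.3: "procedure and/or product related adverse events (AE's) through 12 months following the initial NKA injection". In the same places the primary efficacy outcome is tied to the second injection and runs to 6 months after it. The secondary objective, on renal-specific adverse events, is given 12 months from the first injection. The laboratory measure listed beneath it runs 12 months from the last injection in this protocol.

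On spacing, the synopsis states: "All enrolled subjects will be treated with up to two injections of NKA at least 6 months apart". Section 11.4 fixes the timing: "The month 6 visit should occur -14 to -10 days before second injection and within 3 days of 6 months post first injection". The synopsis also allows delay, with no stated limit: "Under certain circumstances a patient or investigator may decide to postpone or withhold the second dose".

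On follow-up, the synopsis and section 9 plan "18 months in the post follow up phase with 6 months after first NKA injection and 12 months after second NKA injection".

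On recording, section 13.3.1 collects every adverse event from injection to Month 12. From Month 12 to Month 18 it collects those that are related, severe or life-threatening, or CKD-related. Section 14.7.2 summarises treatment-emergent events by relationship up to 18 months after injection, without saying which injection.

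**The concern.** A new patient is planned to receive two injections, and experience with a second injection is one of the things this trial adds. The primary safety clock nevertheless starts at the first injection and is not extended by the second. Every month between the injections comes off the time for which the second is observed in the primary outcome.

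As defined, a related event that starts late in the follow-up after the second injection does not count in the primary safety result, although the trial collects it. A reader of the primary result could take it to describe 12 months of safety after the full treatment course, when it describes less than half of that. The secondary renal-specific objective has the same limit and does not match its own laboratory measure.

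The word *initial* is also undefined for patients returning from the Phase 1 studies.

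**Working it through.** **Inputs**
- End of the primary safety window: 12 months after the initial injection (synopsis, 7.1, 14.2, 14.3).
- Minimum spacing of injections: 6 months (synopsis).
- Second injection on schedule: 10 to 14 days after a Month 6 visit that is held within 3 days of the 6-month date (11.4).
- Planned follow-up after the second injection: 12 months (synopsis, section 9).
- Average month: 365.25/12 = 30.44 days, so 6 months = 182.6 days.

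**The plan's own figure.** 6 months after the first injection + 12 months after the second = 18 months. This reproduces the stated follow-up phase.

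**Ceiling.** With the second injection at exactly 6 months, 12 - 6 = 6 months remain, and 6/12 = 50%.

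**On schedule.** The second injection falls at 6 months plus (10 - 3) to (14 + 3) days, that is, 6 months plus 7 to 17 days.
- Earliest: 182.6 - 7 = 175.6 days = 5.77 months; 175.6/365.25 = 48.1%.
- Latest: 182.6 - 17 = 165.6 days = 5.44 months; 165.6/365.25 = 45.3%.
- Outside the window: 12 - 5.77 = 6.2 to 12 - 5.44 = 6.6 months.

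A day-by-day calendar check over four assumed start years (2016-2019) gives 44.8% to 48.5%. With the 7-day tolerance that the schedule tables print for monthly visits, the offset is 3 to 21 days and the range is 44.3% to 49.2%.

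**Postponed.** Each month of delay removes 1/12 = 8.3 percentage points. A second injection at month 7 leaves 5/12 = 42%, at month 9 it leaves 3/12 = 25%, and at month 12 or later it leaves 0%.

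Some delay is foreseeable. Second injections in different patients must be at least 21 days apart, while first injections are not staggered. The on-schedule range spans only 17 - 7 = 10 days, so two patients whose first injections are less than 21 - 10 = 11 days apart cannot both keep to the 11.4 timing.

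**Comparison with 14.7.2.** If its 18 months count from the first injection, it covers (365.25 - 17)/365.25 = 95.3% to (365.25 - 7)/365.25 = 98.1% of the 12 months after an on-schedule second injection.

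**Returning patients.** Section 6 reports 7 patients injected so far, so at most 7 of the 30 can be returning. They receive one injection here. If *initial* means the first injection under this protocol, they have a full 12 months after their second lifetime injection, and the 50% ceiling does not apply to them.

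**The case against.** The strongest case for leaving the text alone has four parts.

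- **The objective does not promise it.** The mention of two injections belongs to the clause on stabilising renal function. The safety clause speaks of NKA in one kidney. That is a fair reading, and it means that the plan breaks no explicit promise. It does not explain why the secondary laboratory measure follows the last injection while the safety outcomes follow the first.
- **Month 12 is a natural cut.** For new patients it is nominally 6 months after the second injection, where primary efficacy ends and where recording of all adverse events gives way to selective recording. This is a plausible reason for the design. On schedule, however, primary safety closes 7 to 17 days before primary efficacy does, and the events at issue here, the related ones, are still recorded after Month 12.
- **The practical effect is small.** Section 14.7.2 tabulates related events to 18 months, no inferential safety statistics are planned, and neither the DSMB's review of related events nor the stopping criteria have a 12-month limit. Early procedural events fall inside the window unless the second injection is long delayed. All of this stands and limits the harm. It does not correct the declared primary outcome.
- **A longer window makes totals unequal.** This also stands, and the analysis has to allow for it.

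Three stronger readings are tempting, and the documents do not support them.

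- *The ceiling applies to every patient.* It does not hold for returning patients on the natural reading of *initial*.
- *Returning patients have no coverage at all.* A reader might take *initial* to mean the Phase 1 injection. Section 6.3.4 says of the Swedish study "The study was terminated due to a lack of funding on December 10, 2014" and gives the same date for the US study, so a 12-month window would have closed by 10 December 2015. But adverse-event recording starts at this study's consent (13.3.1), enrolment is at injection in this study (10.1), and treatment-emergent events start at enrolment (14.7.2). A window that closed before enrolment would be empty, so this reading is strained. A definition is enough to exclude it.
- *Half of the safety events are lost.* The percentages are shares of follow-up time, not of events, and the events are recorded.

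**Conclusion.** The point holds for new patients who receive both injections under this protocol. The primary safety outcome covers at most 6 of the 12 months planned after the second injection, 5.4 to 5.8 months (45-48%) on schedule, and none if that injection comes at month 12 or later. The 50% ceiling needs only the minimum spacing. The 45-48% range also assumes the 3-day tolerance in 11.4.

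The 12-month denominator is the figure in the synopsis and section 9. Section 11.4 elsewhere says "Patients who complete all visits including all of the follow-up visits will return at 18 months following second injection for the EOS visit". Against 18 months the on-schedule share would be 165.6/547.9 = 30% to 175.6/547.9 = 32%.

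The secondary renal-specific adverse-event objective has the same defect. For returning patients the fault is only an undefined word. The definition should be corrected, but no data are lost and the supporting summaries reduce the consequence.

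**What to change.** 1. In the synopsis, 7.1, 14.2 and 14.3, define the primary safety outcome and the secondary renal-specific adverse-event objective as running from the first injection under this protocol to 12 months after the patient's last injection under it, whether that is the only one or the second. The secondary laboratory measure already uses this anchor. The change also settles *initial* for returning patients, and it leaves the window unchanged for anyone injected once in this trial.
2. Tabulate related adverse events separately after the first and after the second injection.
3. Name the anchor injection in 14.7.2.
4. Make the planned comparison of single- with twice-injected patients over equal time since injection, or as events per patient-time.

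**Cost.** This is mainly wording. The primary safety readout would come about 12 - 6 = 6 months after the primary efficacy window closes. Total windows would be 12 months for one injection and, on schedule, 18 months plus 7 to 17 days (about 18.2 to 18.6 months) for two, hence item 4. If Month 18 counts from the first injection, related-event recording must run 7 to 17 days longer on schedule, and longer after a postponed second injection.

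The inconsistencies in serious-adverse-event recording, in the end-of-study anchor and in the 14.7.3 laboratory window are separate points, to be reconciled separately.
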